8.2.5 Liver Biopsy

A maximum of 3 liver biopsies will be performed including one at Screening.

To minimize the burden on patients, all efforts should be made to perform the first liver biopsy (at Screening 2) after confirmation of the other eligibility criteria. In case of initial screening failure, the liver biopsy, if any, may be re-used for re-screening if not older than 3 months.

The second biopsy will occur at the end of the first year post-VTX-801 administration and the third one will occur at the end of the third year post-VTX-801 administration.

Liver biopsy will be conducted according to institutional standards. The instructions for sample collection, specimen preparation, handling, storage and shipping are described in the Laboratory Manual.

For each biopsy, 2 passes for each timepoint are required as long it is technically feasible.

Protocol VTX-801_CLN_001	Investigational Product: VTX-801
	Version: 9 dated 07 AUG 2023
	Author: Aixial Group CRO

Table 14 Liver Biopsy Related Tests to be Performed by Specialized Central Laboratories

Analysis/Tests

 • Standard liver histology analysis • In situ hybridization for detection of VTX-801 positive cells • Tissue copper content

After planned analyses have been performed, unused biopsy material located at the Central Laboratories may be used for unplanned biomarker explorations (except genotyping) as data emerges; this will be the subject of an optional approval by patients in the informed consent (tick box).

An additional biopsy should be performed in case of suspected DILI with ALT or AST $\geq 5 \times$ ULN (cf. Sections 6.3 and 7.5.2).

Note: All efforts should be made to collect liver biopsies for each patient as described in the schedule of events. However, for the dose escalation cohorts only, if a patient declines to have liver biopsies taken, these can be replaced with Fibroscan®. Should Fibroscan® be used instead of liver biopsy at Screening, this should be implemented for the rest of the study, to ensure consistency for the longitudinal analysis.

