Sirolimus level test: sampling for blood trough concentration 4-5 days after starting treatment with Sirolimus	Section 7.5
[REDACTED]	[REDACTED]
24-hour urinary copper (to end prior to radiocopper administration)	Section 8.1.13
[REDACTED]	[REDACTED]
Radiocopper administration (around 9 am)	Section 7.4
[REDACTED]	[REDACTED]
[REDACTED]	[REDACTED]
[REDACTED]	[REDACTED]
Adverse events	Section 9.2
Prior medications	Section 8.1.2

Refer to Table 2 Summary of Schedule of Events: Baseline to Week 12				
Visit 4	Day -2	Pre VTX-801	In or Out-patient visit	Cross-reference
Vital signs				Section 8.1.4
Sirolimus				Section 7.5
[REDACTED]				[REDACTED]

Protocol VTX-801_CLN_001	Investigational Product: VTX-801
	Version: 9 dated 07 AUG 2023
	Author: Aixial Group CRO

[REDACTED]	[REDACTED]
Adverse events	Section 9.2
Concomitant medications	Section 8.1.2

Refer to Table 2 Summary of Schedule of Events: Baseline to Week 12				
Visit 5	Day -1	Pre VTX-801	In or Out-patient visit	Cross-reference
Vital signs				Section 8.1.4
Weight				Section 8.1.3
Sirolimus				Section 7.5
[REDACTED]				[REDACTED]
Vector shedding: blood, urine, saliva, feces - mandatory				Section 8.2.3
Vector shedding: At Day -1 baseline starting after last radiocopper sampling				Section 8.2.3

Protocol VTX-801_CLN_001	Investigational Product: VTX-801
	Version: 9 dated 07 AUG 2023
	Author: Aixial Group CRO

and within 24 hours before VTX-801, taking into account +7D window for administration. These assessments are to be performed either at V5 or V6.	
Adverse events	Section 9.2
Prior medications	Section 8.1.2

10.3 Visit 6: Day 1, Week 1

This is the first day of the inpatient period related to VTX-801 administration. The patient will then be hospitalized overnight and will be discharged on the following day.

If the patient's medical status post-VTX-801 administration necessitates a prolonged hospitalization, please refer to Section [9.3](#) Serious Adverse Events.

Flexibility of up to 7 additional days for VTX-801 administration is allowed if needed in order to comply with radiocopper production constraints or to accommodate the sites and/or patients.

Home nurse collected samples for liver biochemistry panel may be sent to the Central Laboratory instead of to the Local laboratory.

Refer to Table 2 Summary of Schedule of Events: Baseline to Week 12				
Visit 6	Day 1 + 7 days	VTX-801	Inpatient visit	Cross-reference
Special instructions:				Section 7.2

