5.4 Other Data Analyses Considerations

Centre Effect Management

Not Applicable.

Subgroup Analyses

Not Applicable.

Other Strata and Covariates

Not Applicable.

Multiple Comparisons and Multiplicity

Not Applicable.

6 Analysis Sets

Analysis sets to be used for the analyses are described in the table below.

Table 2: Analysis Sets

Analysis Set	Description
Screened set	The Screened set will include all patients who were enrolled (signed informed consent) regardless of whether they received the study drug or not.
Safety set	The Safety set will include all patients who received at least part of the VTX-801 dose. This analysis set will be used for all safety analyses.
Pharmacodynamics set	The Pharmacodynamics set will include all patients who received at least part of the VTX-801 dose and who have at least one post-baseline pharmacodynamics assessment (free serum Cu (CuEXC and ANCC), REC, RAC, total serum Cu, 24-hour urinary Cu and serum ceruloplasmin by enzymatic activity assay and by nephelometry).
Efficacy set	The efficacy set will include all patients who received at least part of the VTX-801 dose and who have at least one post-baseline radiocopper assessment.

Given that the study was early terminated and an abbreviated CSR focusing mostly on safety data will be prepared, Pharmacodynamics Set and Efficacy Set will not be used in any analysis.

7 Methods of Analysis

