7.9 Safety Analyses

All safety analyses will be performed using descriptive statistics by cohort and overall using the SAF, unless otherwise specified.

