7.9.1 Adverse Events

Adverse events (AEs) will be coded using MedDRA dictionary.

AEs will be graded according to the National Cancer Institute – Common Terminology Criteria for Adverse Events (NCI-CTCAE) version 5, based on study protocol.

The following definitions will be used:

- Treatment-emergent AEs (TEAEs): AEs that occurred during on-treatment period, from the day of VTX-801 dosing,
- Related AEs: AEs suspected by the Investigator to have a relationship to study treatment (as recorded on the AE eCRF page, Relationship to VTX-801 = Possibly related, Probably related, Definitely related or missing,
- Serious Adverse Events (SAE): serious AEs (as recorded on the AE eCRF page, Does AE Meet the Definition of an SAE = Yes),
- AEs leading to Death: adverse event leading to death (as recorded on the AE eCRF page, Results in death, or Outcome = Fatal, or Grade = 5),
- Liver function AEs: adverse event meeting the definition of a suspected DILI (as recorded on the AE eCRF page, does AE meet the definition of a suspected DILI event? = Yes).

An overview summary table will present the number and percentage of patients with a TEAE, including:

- TEAEs / TEAEs related to study treatment,
- Serious TEAEs / Serious TEAEs related to study treatment,
- Liver TEAEs / Liver TEAEs related to study treatment,

- Adverse events of special interest (AESI) / AESI related to study treatment,
- Dose Limiting Toxicity / Dose Limiting Toxicity related to study treatment,
- TEAEs leading to death / TEAEs related to study treatment leading to death,
- TEAEs with NCI-CTCAE grade ≥ 3 / TEAEs related to study treatment with NCI-CTCAE grade ≥ 3 ,
- TEAE meeting any stopping rule,
- TEAE Related to Radiocopper Administration,
- TEAE related to Other Study Procedure.

In addition, the following tables will be produced by SOC and PT:

- TEAEs / TEAEs related to study treatment,
- Serious TEAEs / Serious TEAEs related to study treatment,
- Liver TEAEs / Liver TEAEs related to study treatment,
- TEAEs and maximum CTCAE grade / TEAEs related to study treatment and maximum CTCAE grade,
- TEAEs leading to death / TEAEs related to study treatment leading to death,
- Non-serious TEAE.

A patient with multiple occurrences of an AE will be counted only once in the AE category. SOCs will be sorted by descending order of frequency for the overall group, PTs will be sorted by descending order of frequency for the overall group within each SOC.

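### The radiocopper and study-procedure rows of the AE overview count only from VTX-801 dosing, so events that start earlier, after the Day -3 injection or a screening biopsy, are listed but not tabulated

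*SAP*

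**What the plan says.** SAP 7.9.1 plans an overview table of patients with a treatment-emergent adverse event. Two of its rows are "TEAE Related to Radiocopper Administration" and "TEAE related to Other Study Procedure". The same section defines the events that count: "Treatment-emergent AEs (TEAEs): AEs that occurred during on-treatment period, from the day of VTX-801 dosing". Every table by system organ class and preferred term in 7.9.1 is also restricted to treatment-emergent events, including those for serious events and for events leading to death.

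The population comes from SAP 7.9: "All safety analyses will be performed using descriptive statistics by cohort and overall using the SAF, unless otherwise specified". SAP section 6 (Table 2) defines that set: "The Safety set will include all patients who received at least part of the VTX-801 dose". The same table defines a Screened set, but 7.9 assigns no AE output to it.

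SAP 7.9.1 also provides listings of all AEs (with pre-treatment events identified), of serious and non-serious AEs, and of deaths. It names no analysis set for them.

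The protocol collects the events at issue. Section 9.2.6 (Table 16) captures procedure-related AEs from consent and all AEs from Screening 2. Section 9.2.3 requires a causality judgement against radiocopper and against study procedures.

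**The concern.** The two rows describe risks from exposures that start before VTX-801, but they count from VTX-801 dosing. The first radiocopper injection is at Visit 3, Day -3 (protocol 10.2). On biopsy, protocol 8.2.5 says: "A maximum of 3 liver biopsies will be performed including one at Screening". An acute reaction to that first injection, or a complication of that biopsy, would normally start and be recorded before dosing.

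Safety is the primary endpoint, and the abbreviated report focuses on it. Protocol 2.5 names both radiocopper and repeated liver biopsies as sources of risk. A reader who sees zero in either row could conclude that no such event occurred. The row supports only a narrower statement: none started on or after the dosing day in a dosed patient.

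**Working it through.** The documents give no figure on this point, so there is none to reproduce. The check traces each AE output to its event window and population, then sizes the part left out.

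**1. Window and population**

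| Output (SAP 7.9.1) | Event window | Population |
|---|---|---|
| Radiocopper row, procedure row | From dosing day | Safety set (dosed) |
| All tables by system organ class and preferred term | From dosing day | Safety set (dosed) |
| All-AE, serious and non-serious AE listings | Pre-treatment included in the all-AE listing; no window stated for the other two | Not stated |
| Death listing | All deaths and on-treatment deaths | Not stated |

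**2. Radiocopper injections.** Three are planned per patient: Day -3, Week 12 and Week 36 (protocol 4.2, 7.4.4).

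- Share before dosing: 1/3 = 33%.
- For the 4 dosed patients (SAP section 9): 4 of 4 × 3 = 12.
- Protocol 10.5.13 allows for Week 36 radiocopper not taking place. If nobody received it, the share is 4 of 4 × 2 = 8, or 50%.

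The documents do not say how many injections were given. The range assumes that each dosed patient had at least the Day -3 and Week 12 injections.

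**3. Radiocopper activity left when counting starts.** The half-life is 12.7 h (protocol 7.4.1), so the fraction remaining is 0.5^(t/12.7).

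- Day -3 to Day 1 is 3 days, because there is no Day 0: t = 72 h, 72/12.7 = 5.67 half-lives, fraction 0.0197, about 2.0%.
- With the full 7-day allowance for VTX-801: t = 72 + 168 = 240 h, 18.9 half-lives, fraction 0.000002, about 0.0002%.

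Almost all of the first radiocopper exposure is over before the row begins to count.

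**4. Biopsy.** Up to three are planned: screening, end of Year 1 and end of Year 3 (protocol 8.2.5). The Screening 2 window is Day -49 to Day -14, with 5 days' tolerance (protocol 10.1.2), so the screening biopsy is wholly pre-dose. The share is up to 1/3. It is an upper limit because a patient in an escalation cohort who declines biopsy may have Fibroscan instead, and all 4 dosed patients were in escalation cohorts.

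**5. Illustration with assumed risks.** The documents give no event rate. Let p be an assumed, independent risk per injection of a radiocopper-related event that starts before the next milestone.

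| Assumed p | Patient risk, post-dose injections only: 1-(1-p)² | Patient risk, all three: 1-(1-p)³ | At least one of 4 patients has a pre-dose event: 1-(1-p)⁴ |
|---|---|---|---|
| 5% | 9.8% | 14.3% | 18.5% |
| 10% | 19.0% | 27.1% | 34.4% |
| 20% | 36.0% | 48.8% | 59.0% |

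The last column is the chance that the row omits at least one event in the dosed patients.

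**6. Serious events and deaths.** Protocol 11.4.4.1 says that deaths and SAEs will be tabulated by system organ class and preferred term, and does not repeat the treatment-emergent condition there. SAP 7.9.1 tabulates only serious treatment-emergent events and treatment-emergent events leading to death. SAP section 9, which lists changes from the protocol, does not mention this.

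**The case against.** Four counter-arguments carry weight.

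- **The events are not lost.** The all-AE listing identifies pre-treatment events, and there are separate serious AE and death listings. This stands: for dosed patients the gap is in tabulation, not in reporting.
- **The SAP largely follows the protocol.** Protocol 11.4.4.1 summarises treatment-emergent events and lists the rest, and 11.4.4 presents safety results for the Safety Analysis Set. This stands for the two rows, which are a design gap and not a departure. It is weaker for SAEs and deaths. There the protocol sentence could be read as inheriting the condition from the paragraph before it, but it does not say so.
- **The rows are labelled as treatment-emergent.** True, but that clock belongs to VTX-801. The label does not tell a reader that the first injection is outside it.
- **Some pre-dose exposures do contribute.** An event attributed to the Day -3 injection or to the biopsy counts if it starts on or after the dosing day. It also counts if its start day is missing and falls in the dosing month, because SAP 5.2 sets such dates to the dosing date.

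A reader might go further and infer that undosed patients appear in no AE output at all. The documents do not establish this. The Safety set default in SAP 7.9 is worded for descriptive analyses. Several listings in 7.9.4 are explicitly placed on the Safety set, and listings in 7.3 and 7.4 are explicitly for all patients. The AE listings say neither, and the table and listing shells are a separate document. The documents also report no patient who was biopsied or given radiocopper and then not dosed, although protocol 10.10 provides for withdrawal between Visit 2 and dosing.

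**Conclusion.** The point holds as a gap in tabulation. Events that start before dosing and are attributed to the Day -3 radiocopper injection or to a screening biopsy are left out of the two rows named for those risks and out of every table by system organ class and preferred term. The exposure outside the window is 1 of 3 planned injections per patient (1 of 2 if Week 36 was not given) and up to 1 of 3 planned biopsies. The analysis set for the AE listings is unstated. The narrowing of the SAE and death tables is not recorded as a change.

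Two stronger readings of the size are not supported. The 33% is a share of planned procedures, not of adverse events; no event rate is given. Nor can it be said that the screening biopsy is the only planned one for a patient who stops before Year 1. Protocol 10.10 says that the early termination visit is the end-of-Year-1 visit, which includes a biopsy, but its own itemised list omits it.

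With 4 dosed patients the listing can be read case by case, so the practical effect is modest. This is a should-fix. The separate DMC analysis plan and the output shells are not among the documents and could change the picture.

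**What to change.** In SAP 7.9.1, redefine the two rows:

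- AEs related to radiocopper, with onset from first radiocopper administration.
- AEs related to other study procedures, with onset from informed consent.

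Show pre-dose and post-dose counts separately in each, so that the treatment-emergent count stays visible. For the dosed patients the radiocopper row would then cover 12 planned injections instead of 8, or 8 instead of 4 if Week 36 was not given.

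State that the AE, SAE and death listings use the Screened set, with a flag for patients who were never dosed and, among them, those who received radiocopper.

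For SAEs and deaths, either tabulate all of them as the protocol wording allows, or record the restriction to treatment-emergent events in SAP section 9.

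The cost is SAP wording and minor re-programming of two rows and a few listings. The onset dates and causality judgements are already collected, and trial conduct does not change.

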7.9.2 Clinical Laboratory Evaluation

All laboratory data collected will be reported using standards units.

Sponsor: Vivet Therapeutics, SAS
Protocol: VTX-801_CLN_001
SAP: 1.0 / 24Jan2025

The continuous numerical measurements of all laboratory tests will be summarized using descriptive summary statistics for each visit, by dose cohort and overall. A listing of laboratory parameters will be created.

Also, results of pregnancy tests will be listed.

7.9.3 Vital Signs

All vital signs parameters collected will be reported in a listing.

7.9.4 Other Safety Data

Electrocardiogram (ECG)

All ECG parameters collected will be reported.

The numerical measurements and change from baseline of ECG parameters will be summarized by timepoint using descriptive summary statistics for each visit, by dose cohort and overall. ECG parameters will also be provided in a listing.

Ophthalmology

A listing of all ophthalmological examination assessments will be created on the SAF.

Sirolimus

Sirolimus assessments will be reported in listings on the SAF.

Radiocopper administration

Radiocopper administration will be reported in a listing on the SAF.

Steroids:

Per protocol steroid treatments will be reported in a listing on the SAF.

[REDACTED]

[REDACTED].

Vector shedding:

Vector shedding findings will be reported in a listing on the SAF.

Brain and abdominal MRI:

Brain and abdominal MRI assessments/findings will be reported in a listing on the SAF.

Physical examination:

Physical Examination includes the following parameters: General appearance, Skin, Head and neck, Eyes, ears, nose, throat, Lymph node palpation, Lungs, Chest, Abdomen, Extremities, Neurological function.

A listing of physical examination evaluations will be created on the SAF.

8 Interim Analysis (IA)

8.1 Planning of Analyses

This SAP covers the interim and final analyses for the study.

A separate SAP has been developed specifically for the safety reviews to be conducted by the DMC.

Given that the treatment was early terminated, an abbreviated CSR focusing on safety will be prepared based on the interim analysis. Thus, the SAP is written with focus on safety and other important data for reporting purposes.

The final analysis will occur at the end of the safety follow-up and will support the writing of a CSR addendum.

8.2 Planned Interim Analysis Details

An interim analysis was planned to occur 1 year after the last patient was treated with VTX-801, per protocol. Due to the treatment premature discontinuation, the IA will occur before the 1-year period is reached after the last patient is treated with the study drug. Also, the IA will mainly focus on safety data.

9 Changes from Study Protocol

Due to early termination of the treatment, below is the list of changes from protocol:

- When the decision has been made to early terminate the treatment phase of the study, only 4 patients were dosed from US sites (2 in cohort 1 and 2 in cohort 2),
- The interim analysis will cover the study up to the early termination visit, occurring prior the end of the 1 year period after last patient was treated,
- The final analysis will cover the safety follow-up period after the study was prematurely discontinued,
- Pharmacodynamics Set and Efficacy Set will not be used for any of the TFLs,
- Pharmacodynamics and efficacy analysis will be limited to descriptive statistics,
- SoC withdrawal related data will not be produced,
- Shift tables will not be produced for laboratory evaluations,
- MELD has been calculated with an outdated formula. Footnote will be added to MELD-related outputs for reader's information.

10 References

- [1] ICH guidelines - E9: Statistical Principles for Clinical Trials, Adopted in EU by CPMP, March 1998, issued as CPMP/ICH/363/96
- [2] ICH guidelines - E3: Structure and Content of Clinical Study Reports, Adopted in EU by CPMP, December 95, issued as CPMP/ICH/137/95

11 Appendices

11.1 Tables, Figures and Listings

Tables, figures and Listings (TFLs) shells are presented in a separate document.

Sponsor: Vivet Therapeutics, SAS

Protocol: VTX-801_CLN_001

SAP: 1.0 / 24Jan2025

11.2 Other

Not Applicable.
